As an amendment to the original protocol, this research also includes computational analysis of language. Recent developments in the automated analyses of language have shown promising findings in identifying computational measures of language to characterize thought disorder in schizophrenia. However, most of the research to date has focused on measure of incoherence and little attention has been paid to other central features of language in schizophrenia such as poverty of content. This additional research protocol aims to measure “semantic density” through the use of machine learning and Natural Language Processing. It also aims to detect latent semantic content reflective of the psychopathology of thought disorder in schizophrenia. The resulting linguistic findings can be potentially analyzed in conjunction with other biomarkers and future findings of the original study.

4. Objectives

Objective 1. Determine the impact of inflammation on reward processing in patients with schizophrenia using functional magnetic resonance imaging (fMRI).

Hypothesis 1: Increased peripheral blood markers of inflammation will be associated with decreased activation of reward-related ventral striatal regions and decreased connectivity between the ventral striatum and medial prefrontal cortex using whole brain analysis.

Dependent variables:

Immune Markers: Peripheral inflammatory markers: plasma CRP, IFN-alpha, IL-6, sIL-6R, IL-10, TNF-alpha, sTNFR 1 and 2, IL-1 beta, IL-1ra, sIL-2R, and MCP-1

Neuroimaging Tasks: Degree of functional connectivity between the striatum and other brain regions on resting state scan (Z scores); performance on fMRI tasks (see below)

Objective 2. Determine the impact of inflammation on objective and clinical measures of motivation and negative symptoms in patients with schizophrenia.

Hypothesis 2: Increased inflammation will be associated with increased impairment in objective and clinical measures of motivation and negative symptoms.

Dependent variables:

Immune Markers: Peripheral inflammatory markers: plasma CRP, IFN-alpha, IL-6, sIL-6R, IL-10, TNF-alpha, sTNFR 1 and 2, IL-1 beta, IL-1ra, sIL-2R, and MCP-1

Behavior: Scores on the: Positive and Negative Symptom Scale (PANSS); Brief Negative Symptom Scale (BNSS); Snaith Hamilton Pleasure Scale (SHAPS); Inventory of Depressive Symptomatology (IDS-SR), Childhood Trauma Questionnaire (CTQ); Motivation and Pleasure Scale (MAPS-SR)

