Effort-Expenditure for Rewards Task (EEfRT): The EEfRT task is a multi-trial game in which participants are given an opportunity on each trial to choose between two different task difficulty levels in order to obtain monetary rewards.¹⁰⁹ For all trials, participants make repeated manual button presses within a short period of time. Each button press raises the level of a virtual "bar" viewed onscreen by the participant. Participants are eligible to win the money allotted for each trial if they raise the bar to the "top" within the prescribed time period. Each trial presents subjects with a choice between two levels of task difficulty, a 'high effort' and 'low effort' task that require different amounts of speeded button pressing. Reward magnitudes for the high effort task will vary between \$1 and \$10, while reward magnitudes for the low effort task remain constant (between \$0.50 and \$1.00). The reward magnitudes will be decided at the discretion of the PI. Trials will also vary in terms of 3 levels of probability of winning the amount associated with the choice selected. Subjects participate in the task for approximately 20 minutes and the first 50 trials are used for analysis. Because of the requirement for rapid button presses for a long period of time, we will exclude participants who report chronic pain in their wrists/hands and or those who have wrist/hand injuries, such as Carpal Tunnel Syndrome. At the discretion of the PI, the EEfRT may be repeated after the neuroimaging scan.

Neuroimaging Tasks:

The PI will choose which of these fMRI tasks will be performed at the fMRI study visits.

Monetary Incentive Delay (MID) Task: Assessment of reward anticipation will be achieved using the MID task.^{26,110-112} Briefly, during this task participants have the opportunity to win or lose money by making a rapid button press in response to a target visual stimulus. The primary epoch of interest is the “anticipatory delay” – a period of ~2000ms that occurs after participants have been informed how much money they can win or lose on a given trial, but prior to the presentation of the target. This epoch has repeatedly been associated with robust ventral striatal activity.^{26,110,113-114} Participants will complete 2 functional runs of between 50 and 200 trials each (the number of trials will be decided at the discretion of the PI), with evenly distributed reward magnitudes between \$0.20 and \$10.00, to be decided by the PI.

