Magnetic Resonance Imaging: At Part A Visit 2 and Part B Post Infusion Visit 1, MRI experiments will be performed on a 3T MRI scanner (either at the BITC Research Scanner at the Emory University Hospital, the Department of Psychology Facility for Education and Research in Neuroscience (FERN) or the Center for Systems Imaging (CSI) at Wesley Woods, to be decided by the PI prior to the start of the study. Only one scanner will be used throughout the course of study to maintain consistency). The subject will be pre-screened with the "MRI Screening form" to confirm that he/she is eligible to participate in the scan. Because MRI scanning can affect metallic and other implants, all subjects will be careful screening for metallic implants and other contra-indications to MRI prior to the procedure, using the standard Emory University Biomedical Information Technology Center MRI screening form. Subjects with contra-indications will not receive a MRI

scan. The MRI scanner is an enclosed space and subjects may experience claustrophobia while being scanned. Should a subject develop claustrophobia during the procedure, the scan will be terminated. All subjects will be required to limit caffeine intake for two hours prior to the scan. Any food or drink intake during this time frame will be recorded using a MRI Scan Food, Drink and Cigarette Intake Form immediately prior to the scan. Subjects will be offered an opportunity to be scanned with one of two scanning protocols. Depending on which protocol they choose, the scan may take between 60 to 90 minutes in length, though will not exceed one and a half hours. The patients will be informed of the time requirements prior to participation in the study. Protocol one would include the following scans: Structural Scan (~6 minutes), Resting State Scan (~ 8 minutes), Diffusion Tensor Imaging Scan (~6 minutes), Task-Based Scans (~24 minutes). Protocol two would be similar though would allow for a break between the Diffusion Tensor Imaging Scan and the Task-Based Scans where the subject would be allowed to exit the scanner, rest, go to the bathroom, and drink water, should they choose. This second protocol will be longer in total time given the break. Figure 4 details the two proposed scanning protocols.

Figure 7: Scanning Protocol Options

Scanning Protocol One		Scanning Protocol Two	
0:00*	Enter Scanner	0:00*	Enter Scanner
5:00	Symptom Check	5:00	Symptom Check
6:00	Start Scan	6:00	Start Scan

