Objective 1: The first-level individualized design matrices for each participant will be estimated using a general linear model. Effects of task (see above contrasts) will be computed on a voxelwise basis for each participant in the form of statistical parametric maps of discrete contrasts. Subsequent second level paired t test analyses will be performed on the SPM contrast images. Between-subject effects of task and individual inflammatory marker concentrations (beginning with CRP) will be determined using regression analysis. For the resting state and task based functional connectivity analysis, whole brain, subject-level correlation maps indicating regional similarity with the striatal seed region time series will be generated and Fisher transformed to Z-score maps. In addition, data reduction strategies will be employed to address inflammatory marker collinearity in analyses combining relevant inflammatory markers. To assess significance of correlated activity with each bilateral seed region, paired t-tests will be conducted on participants' Z-score maps, adjusted for multiple comparisons. For significant brain regions, descriptive statistics will be used to characterize the mean, standard deviation, and standard error of the Z scores. Relevant covariates, which may be associated with alterations in functional connectivity or task performance, include body mass index (BMI), age, sex, education, nicotine use, antipsychotic dose (as measured by chlorpromazine equivalents), use of other medications, as well as depression, and will be included in the analyses as appropriate.

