Region of Interest (ROI) seed placement and connectivity analysis: 8 basal ganglia seeds (4 per hemisphere) will be used representing regions of the ventral and dorsal striatum as defined in Montreal Neurological Institute (MNI) space. In each hemisphere, seeds will be comprised of a spherical mask with a 6 mm radius centered on the ROI. The ventral striatum will be defined by coordinates ($\pm 14, 5, -4$) from a previous fMRI study in IFN-alpha-treated subjects demonstrating maximal decreases in response to a hedonic reward task. The other 3 regions, ventral rostral putamen ($\pm 20, 12, -3$), dorsal caudate putamen ($\pm 28, 1, 3$), and dorsal caudate ($\pm 13, 15, 9$), will be defined according to Di Martino et al. 2008 and other studies assessing functional connectivity with the striatum,¹¹⁷⁻¹¹⁹ and consistent with identified subdivisions of the striatum. Whole brain, subject-level correlation maps indicating regional similarity with the seed region time series will be generated and Fisher transformed to Z-score maps. To assess significance of correlated activity with each bilateral seed region, I will conduct paired t-tests on participants' Z-score maps. To correct for multiple comparisons, resulting maps will be cluster corrected ($p < 0.05$ whole-brain correction, with a height threshold of $p < 0.001$, uncorrected), using SPM12.

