Objective 2: Descriptive statistics will be used to characterize the mean, standard deviation, and standard error for each of these clinical and behavioral measures. For the EEfRT, proportion of hard-task choices across each level of probability as well as the difference between the proportions of hard task choices in low and high reward probabilities (effort allocation) will be calculated. Lower proportions of hard task choices indicate decreased motivation for monetary rewards. A larger difference in the proportion of hard task choices reflects more effort allocation. Regression analyses will be conducted to examine the relationship between task performance and concentrations of inflammatory markers (beginning with CRP). Regression analyses examining the relationship between changes in functional connectivity (Z scores) obtained using fMRI and changes in behavior and neuropsychological performance will also be conducted. In cases where data are not normally distributed, we will use standard transformation procedures to achieve normality, and/or use non-parametric tests of significance. The same covariates and data reduction strategies described above will be used in these analyses.

Objective 3: Formal mediation analysis will be conducted to assess whether functional connectivity mediates

the relationship between inflammation (as measured by inflammatory marker concentrations – beginning with CRP) and behavior (clinical ratings and objective measures, as described above). Bootstrapping will be used to provide an empirical estimate of the sampling distribution for indirect effects and will be used to generate confidence intervals for the purpose of inferential testing. A model of moderated-mediation will also be tested to assess whether mediation pathways are influenced by the presence of high vs. low baseline inflammation. Path analysis will be implemented using macros developed by Preacher and Hayes (<http://quantpsy.org/medn.htm>), which enable inclusion of covariates as well as possible moderators.

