Optional Study C Aim 1: Relationships between inflammatory and metabolic markers will be examined by linear regression at baseline and pre and post-OGTT. Change in these markers pre and post-OGTT will also be calculated and compared. Cytokines and their soluble receptors, as well as glucose-related markers at baseline, will be combined into a composite score based on the sum of Z-scores for initial analyses, then assessed individually by linear regression models with selection including clinical covariates. Covariates such as sex, age, race and BMI will be explored as potential confounders or mediators in all analyses.

Optional Study C Aim 2: Targeted FC for each subject and condition will be calculated as the degree of correlation in activity between 3mm³ radius spheres placed in four regions of striatum,^{57, 163 142}) that subserve reward processing and other goal-directed behaviors such as motor control,^{117,164} and the vmPFC ROI identified as being reward-sensitive in neuroimaging meta-analyses and as used to define vmPFC in our previous work (MNI coordinates x=0, y=44, z=-8, cluster size=1408 mm³ and encompassing parts of BA11 and ventral BA32 of ACC).^{57,163,165} Z-scores will be extracted for FC values at baseline and pre and post-OGTT. FC will be assessed between bilateral striatal seeds and the vmPFC ROI separately based on our previous work in MDD and IFN- α -induced depression,^{51,57} indicating that effects of inflammation are more pronounced on the left side. Linear regression models will be used to independently examine relationships between inflammation or metabolic dysfunction (Part C, Aim 1) and reward motor pathways. In our previously published work and Preliminary Data, use of inflammatory or metabolic measures as continuous rather than categorical variables were more sensitive for detecting associations with corticostriatal connectivity,⁵⁷ and will be the primary method for assessing relationships between inflammation or metabolism (as independent variables) and motivation and motor pathways (as dependent variables, including FC and behaviors). Covariates such as sex, age, race and BMI will be explored as potential confounders or mediators of relationships between biomarkers, brain and behavior.

8. Adverse Event Reporting

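### Task-run connectivity is a plain seed correlation with no handling of task-evoked signal, so a marker effect on activation alone can appear as a change in connectivity

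*Combined protocol and SAP*

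**What the plan says.** Section 7, Objective 1, sets a single connectivity method for rest and task: "For the resting state and task based functional connectivity analysis, whole brain, subject-level correlation maps indicating regional similarity with the striatal seed region" are produced and converted to Z scores. The seed-placement paragraph that follows repeats it: "Whole brain, subject-level correlation maps indicating regional similarity with the seed region time series will be generated and Fisher transformed to Z-score maps". Neither place mentions residuals from the task model, a PPI term or a beta-series approach. A first-level general linear model is fitted, but only to produce activation contrasts. Activation is not among the listed covariates.

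Hypothesis 1 (Section 4) has two parts: "decreased activation of reward-related ventral striatal regions and decreased connectivity between the ventral striatum and medial prefrontal cortex". The connectivity variable listed for Objective 1 is "Degree of functional connectivity between the striatum and other brain regions on resting state scan (Z scores". A separate run is scheduled for it, "Resting State Scan (~ 8 minutes", and Figure 7 places it before the tasks in both scanning protocols.

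Of the anticipation period in the Monetary Incentive Delay task, Section 5 says: "This epoch has repeatedly been associated with robust ventral striatal activity". The ventral striatal seed is centred on coordinates where interferon-alpha treatment most reduced the response to reward (Section 7, seed placement).

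For Objective 3, "Formal mediation analysis will be conducted to assess whether functional connectivity mediates" the link between inflammation and behavior. The text does not say whether that connectivity comes from rest or task. Hypothesis 3 names neural activation, not connectivity, as the mediator.

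**The concern.** In a task run, two regions that respond to the same reward cues have correlated time series because they share the cue response, even if nothing else couples them. A plain seed correlation mixes that shared response with background coupling. If a marker is related to the size of the striatal response, which is what Hypothesis 1 predicts, it will usually also be related to the raw task-run correlation.

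A single effect on activation could then be reported twice, once as activation and once as connectivity. If task-run values were used in Objective 3, a mediator labelled connectivity could in substance be activation, and the study could claim a circuit mechanism that its data do not show.

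**Working it through.** **The plan's own figure.** The power paragraph gives N=100, r=0.5, two-tailed alpha 0.05 and power above 80%. By Fisher's z, power = Φ(atanh(0.5)·√97 − 1.96) = Φ(5.41 − 1.96) = Φ(3.45) = 99.97%. The statement is true as a lower bound and is not in dispute. N=100 and r=0.5 are reused below.

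**Closed form.** Let seed = b1·task + e1 and target = b2·task + e2, with task and errors of unit variance and corr(e1, e2) = ρ, the background coupling. Then

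raw r = (b1·b2 + ρ) / √[(1 + b1²)(1 + b2²)].

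The task share of a region's variance is b²/(1 + b²), so b = 0.5 means 0.25/1.25 = 20%. The documents give no b or ρ; all values here are assumptions.

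- No coupling (ρ = 0), b2 = 0.5. At b1 = 0.5, r = 0.25/1.25 = 0.20. At b1 = 0.25, r = 0.125/√(1.0625 × 1.25) = 0.108.
- ρ = 0.3 held fixed, seed response falling:

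| Target response | b1 = 0.5 | b1 = 0.25 | b1 = 0 |
|---|---|---|---|
| Co-activated (b2 = 0.5) | 0.440 | 0.369 | 0.268 |
| Unresponsive (b2 = 0) | 0.268 | 0.291 | 0.300 |
| Deactivated (b2 = −0.5) | 0.040 | 0.152 | 0.268 |

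- Strong coupling (ρ = 0.6), weakly co-activated target (b2 = 0.25): reducing b1 from 1.0 to 0.5 raises r from 0.583 to 0.629.

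Coupling is constant within each comparison, yet r moves. The direction depends on the target's response and on ρ.

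**Simulated false associations.** N=100, 360 volumes, CRP-activation correlation −0.5, coupling unrelated to CRP (SD 0.15 on the Z scale), one connection tested at p<0.05.

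- Set A: co-activated regions, TR 2 s, AR(1) noise 0.3, amplitude coefficient of variation 0.4, 200 replicates. Task share 5%, 10%, 20%, 30% gave 10%, 18.5%, 49%, 64.5%. After task regression: 5.5% to 6.5%.
- Set B: mean seed amplitude 0.5 (SD 0.2), mean ρ 0.3, 600 replicates:

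| Scenario | Mean r, CRP vs Z | Raw | Task regressed |
|---|---|---|---|
| Co-activated, only seed falls | −0.17 | 41% | 5.3% |
| Co-activated, both fall | −0.29 | 88% | 6.2% |
| Target unresponsive | +0.06 | 7% | 5.7% |
| Target deactivated | +0.24 | 71% | 3.5% |
| Resting run (no task) | 0.00 | 3.8% | not needed |

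**Effect of a stricter threshold.** The plan's height threshold of p<0.001 with cluster correction is written for the paired t-test maps; none is stated for the marker regression. If that height applied one-sided (critical value 3.09), each rate can be converted by solving for the shift δ that gives it at 1.96, then taking Φ(δ − 3.09). For 49%, δ = 1.935 and Φ(−1.155) = 12%. Set A becomes about 0.7%, 2%, 12% and 22% per voxel. The two co-activated scenarios of Set B become about 9% (δ = 1.74) and 51% (δ = 3.11). Cluster extent is not modelled.

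**The case against.** Four points can fairly be made against this.

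1. **Silence is not refusal.** The plan gives no fMRI preprocessing detail at all: no motion correction, nuisance regression or filtering. Task regression might be done without being mentioned, and the first-level model already supplies the residuals. This is fair as to intent. But the plan does state a method and gives the same one for rest and task; followed as written, it carries activation into the task-run values.

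2. **The named variable is clean.** A reader might infer that the two halves of Hypothesis 1 cannot be told apart. The documents do not support that: resting-state Z scores are the listed connectivity variable, they come from a separate run, and that run contains no task cues. The footnote to Figure 3 makes scan content permissive, so some patients may lack a resting run, but nothing says task values would replace it. Nor is task-run connectivity an error in itself, since the abstract says Aim 1 uses both task and resting imaging.

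3. **The direction is not fixed.** A reader might also infer that any fall in activation lowers connectivity. The closed form shows otherwise. Section 7 (Optional Study C Aim 2) calls the ventromedial prefrontal region reward-sensitive, which makes co-activation plausible, but gives no sign or size for these tasks.

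4. **The rates are not those of the written procedure.** They test one connection at p<0.05, whereas Hypothesis 1 specifies whole-brain analysis, and the inputs are assumed. This stands: the rates illustrate the mechanism and do not forecast the study's error rate.

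Extending the point to Part C would be speculative. There, "Targeted FC for each subject and condition will be calculated as the degree of correlation in activity", but the text does not say that task runs are used, and the power paragraph calls the Part C reward-circuit analyses exploratory.

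**Conclusion.** The point holds for task-run connectivity. As written, that measure combines coupling with activation, so a marker effect on activation alone can appear as altered connectivity: typically a fall for co-activated targets, a rise for deactivated ones. It does not reach resting-state connectivity, and it reaches Objective 3 only if task-run values supply the mediator, which the plan leaves open.

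With co-activated regions, N=100 and a single test at p<0.05, false CRP-connectivity associations ran from about 10% to 88%, against about 4% to 7% across all scenarios once the task was regressed out. These figures rest on assumed task variance, amplitude spread and coupling, and on a CRP-activation correlation of −0.5 taken from the plan's effect size. The possible signs of the bias follow from the closed form and do not depend on the simulations. The plan should be changed, because a stated rule can mislead and a better one is available at little cost.

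**What to change.** - **Section 7, Objective 1 and seed placement:** limit the plain seed correlation to the resting-state run and name it as the test of the connectivity half of Hypothesis 1. For task runs, compute seed correlations on the residuals of the first-level task model, or use a PPI contrast for the anticipation epoch.
- **Section 7, Objective 3:** state that any connectivity mediator is the resting-state value or a task-residual or PPI value, and keep it distinct from the activation mediator named in Hypothesis 3.

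The cost is revised wording and one extra processing step. No new data are needed. A PPI contrast has less power than a raw correlation, so power falls if that option is chosen.

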Neuropsychology: Performance on the Effort Expenditure for Rewards Task (EEfRT), and neurocognitive tasks (see below)

Objective 3. Explore the interrelationship among inflammation, altered reward processing as measured by fMRI, and objective and clinical measures of motivation and negative symptoms in patients with schizophrenia.

Hypothesis 3: Decreased neural activation in reward-related regions will mediate the relationship between inflammatory markers, impaired motivation and negative symptoms.

Immune Markers: Peripheral inflammatory markers: plasma CRP, IFN-alpha, IL-6, sIL-6R, IL-10, TNF-alpha, sTNFR 1 and 2, IL-1 beta, IL-1ra, sIL-2R, and MCP-1

Neuroimaging Tasks: resting state scan; fMRI tasks

Behavior: Positive and Negative Symptom Scale (PANSS); Brief Negative Symptom Scale (BNSS); Snaith Hamilton Pleasure Scale (SHAPS); Inventory of Depressive Symptomatology (IDS-SR); Calgary Depression Scale for Schizophrenia (CDSS), Childhood Trauma Questionnaire (CTQ); Motivation and Pleasure Scale (MAPS-SR)

Neuropsychology: Effort Expenditure for Rewards Task (EEfRT), and neurocognitive tasks (see below)

5. Study Design and Methods

Figure 2: Overview of Proposed Study Visits

Screening Visit Between 9:00 am – 12:00pm	Subject arrives at Grady BHC for consenting and MINI diagnostic interview. They will also complete a physical and psychiatric exam, blood sampling for routine labs, CRP, urine drug screen and pregnancy test. All subjects will be eligible to also complete the MMSE, BNSS, WRAT, and MRI safety screen.
Visit 1	Subjects will be eligible to complete the PANSS, behavioral EEfRT, IDS-SR or SHAPS, and other assessments the PI and study staff may choose from other study visits.
Visit 2 9:00 am	Subject arrives at Emory University Hospital ACTSI suite
9:30 am	Blood Sampling
10:00 am	Behavioral Testing
12:00 pm	Lunch
13:00 pm	MRI Scan
14:30 pm	Complete Study
Visit 3	Complete Behavioral Testing

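### Objective 2 specifies no direct test of inflammatory markers against the clinical scales, and its second regression uses changes in connectivity that Part A does not measure

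*Combined protocol and SAP*

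**What the plan says.** Section 4 (Objectives) states: "Hypothesis 2: Increased inflammation will be associated with increased impairment in objective and clinical measures of motivation and negative symptoms". It then lists the outcomes in two groups. The rating scales and questionnaires come under Behavior: PANSS, BNSS, SHAPS, IDS-SR, CTQ and MAPS-SR. The effort task (EEfRT) and the neurocognitive tasks come under Neuropsychology.

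Section 7, Objective 2, contains three analysis statements:

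- For the scales and tasks together: "Descriptive statistics will be used to characterize the mean, standard deviation, and standard error for each of these clinical and behavioral measures".
- For the markers: "Regression analyses will be conducted to examine the relationship between task performance and concentrations of inflammatory markers (beginning with CRP".
- For imaging: "Regression analyses examining the relationship between changes in functional connectivity (Z scores) obtained using fMRI and changes in behavior and neuropsychological performance".

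The remaining sentences cover EEfRT scoring, transformation or non-parametric tests for non-normal data, and reuse of the covariates and data reduction described for Objective 1. The Power Analysis paragraph also describes the planned correlations as markers against imaging and behavioral tasks, without naming the clinical scales.

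**The concern.** The hypothesis has an objective half and a clinical half, and the written analysis carries only the objective half to a model with a marker in it. The link between inflammation and negative symptoms is in the study title. If its direct test is not written down, the scale, marker, covariates and model can all be chosen after the data are seen. With six listed scales and twelve listed markers, there is a lot to choose from.

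The third statement has a different problem. A regression of change on change needs two connectivity values per person. If the main sample has one, the analysis cannot be carried out as worded, and something unplanned will have to replace it.

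**Working it through.** **1. Match each Objective 2 outcome to an analysis.**

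| Outcome group (section 4) | Descriptive statistics | Regression on markers | Regression on connectivity |
|---|---|---|---|
| Six scales listed as Behavior | yes | none stated | only as change on change |
| EEfRT and neurocognitive tasks | yes | yes | only as change on change |

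Marker regressions specified for the scales under Objective 2: 0 of 6. Two of the six, the IDS-SR (depressive symptoms) and the CTQ (childhood trauma), do not measure motivation or negative symptoms. For the four that do (PANSS, BNSS, SHAPS, MAPS-SR) the count is also zero.

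**2. Match each change to the Part A schedule.**

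- MRI: Visit 2 only (Figure 3). The Magnetic Resonance Imaging paragraph names one other occasion, and that belongs to Part B.
- BNSS: screening only. SHAPS: Visit 1 only. MAPS-SR: Visit 2 only.
- PANSS: Visit 1, or a later visit if it was missed. This is a relocation, not a repeat.
- EEfRT: may be repeated after the scan at the PI's discretion.

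Connectivity therefore has one time point in Part A. A repeated EEfRT could give a change in one task, but there is no change in connectivity to pair with it.

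**3. Reproduce the plan's power statement.** Inputs from Power Analysis: N=100, r=0.5, alpha 0.05 two-tailed, stated power above 80%. By Fisher z:

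- power = Φ(atanh(r)·√(N−3) − 1.960) = Φ(0.5493 × 9.849 − 1.960) = Φ(3.450) = 99.97%. The stated inequality is true.
- N for 80% power at r=0.5: ((1.960 + 0.842)/0.5493)² + 3 = 29.01, so 30 patients.

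**4. What a clinical-scale regression could detect at N=100.**

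- One scale on CRP, 80% power: r = tanh(2.802/√97) = 0.277.
- Adjusted for the eight covariate items listed under Objective 1: r = tanh(2.802/√89) = 0.289.
- Three secondary scales with Bonferroni (alpha 0.05/3), unadjusted for covariates: r = 0.317.
- r=0.30 is not in the plan. Taken as an assumption, power is Φ(0.3095 × 9.849 − 1.960) = Φ(1.088), about 86% for one unadjusted test. It is about 83% with eight covariates, and about 68% with Bonferroni over five outcomes (four scales plus EEfRT; critical value 2.576).

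**5. What happens if no primary test is named.** If tests are independent and unadjusted, family-wise error is 1 − 0.95^6 = 26.5% for six scales on CRP, and 1 − 0.95^72 = 97.5% for six scales on twelve markers. Correlated scales and markers would give lower figures.

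**The case against.** The strongest reply is that Objective 3 already puts clinical ratings and markers in one model, with covariates, and that a mediation model fits the path from marker to outcome as well as the indirect path. This is correct, so a reader who inferred that the plan never relates inflammation to clinical ratings would be wrong. It still does not supply the Hypothesis 2 test. The Precis/Abstract presents Aim 3 as exploratory, and the stated bootstrap inference is on indirect effects. A null indirect effect would not refute an association that may run by another route. The model also needs imaging, which the Study Overview lets staff omit for a subject.

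A second reply is that task performance is loose wording. The Power Analysis sentence, read literally, would also exclude the clinical ratings that Objective 3 includes. That also stands: the sentence cannot prove an intention to leave the scales out. The aims and hypothesis show that the test is intended, so this is most likely a drafting omission.

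On changes, the word might mean differences between people, which would make the regression feasible. The text does not say so. The sentence might also be meant for a part with repeat scans: Part C has pre- and post-challenge scans and its own analysis text, and the current text still refers to a Part B scan although Part B is not described in this version. It is therefore too strong to infer that the regression can be run nowhere. But Power Analysis states that the analyses for all three aims use the 100 patients, and for that sample a within-person change does not exist.

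A reader might also infer that Part A takes a single blood sample. It does not: CRP is drawn at screening and at Visit 2, and the screening value is reserved for classification.

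**Conclusion.** The point holds as a mismatch between hypothesis, design and stated analysis. The clinical half of Hypothesis 2 has no specified direct test under Objective 2, and the change-on-change regression cannot be computed for the Part A sample as worded. It does not follow that the title question is wholly unaddressed, because Objective 3 touches it indirectly. Nor does it follow that the study is too small for the missing test.

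The first conclusion rests on reading task performance as the EEfRT and neurocognitive tasks, which is how section 4 divides the outcomes. The second rests on reading changes as within-person. The detectable correlations assume that 100 patients have both the scale and the marker. Because assessments may be waived, the number may be smaller for some scales.

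**What to change.** Amend Objective 2 in section 7 as follows.

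1. State that clinical scale scores will be regressed on CRP first and then on the other markers, alongside EEfRT performance. Use the covariates already listed under Objective 1, now stated as a definite set, and the transformations already allowed.
2. Name one primary clinical scale, for example BNSS total, with PANSS negative, SHAPS and MAPS-SR secondary under a stated multiplicity rule. The BNSS is an eligibility measure, so nearly everyone should have it. Against that, its entry threshold of 25 narrows the range, and it is taken at screening rather than with the Visit 2 blood sample. The investigators should weigh this when choosing.
3. For Part A, replace changes with the Visit 2 connectivity value and the corresponding behavioral or neuropsychological score. Reserve change scores for the parts with repeat scans: Part C, and Part B if it is still active.

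This costs a few sentences, with no added visits, procedures or patients. It adds a few tests, which the primary scale and the multiplicity rule keep under control.
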